Analyses of treatment effects will be based on the intent-to-treat principle. The first analysis will compare baseline characteristics by randomized treatment assignment to ensure that balance was achieved by the randomization. Characteristics to be examined include known risk factors for cancer and CVD, including age; gender; race/ethnicity; BMI; smoking; alcohol use; physical activity; medical conditions such as hypertension, hyperlipidemia, diabetes, and family history of cancer and CVD; and baseline vitamin D and omega-3 fatty acid levels as assessed by dietary questionnaire in all participants and blood assays in a case-cohort subsample. The large sample size, as well as successful balance of known potential confounders, will provide assurance that unmeasured or unknown potential confounders will also be equally distributed across randomized treatment groups.

In this 2x2 factorial design, the primary aim is to compare the main effects of intention-to-treat with vitamin D softgel capsules and with Omacor® fish oil on cancer and CVD. We will use the Cox proportional hazards model to allow for variable follow-up lengths⁷³ and will estimate the hazard ratio for each intervention using indicators for treatment exposure, controlling for the second intervention, age, and gender. Because the cohort will consist of older individuals, competing risks due to deaths from other causes will be considered. The primary analysis will estimate the cause-specific hazard and the hazard ratio comparing intervention groups for each outcome of interest by censoring individuals with deaths due to competing causes. To estimate the cumulative incidence function, the subdistribution of each endpoint will be plotted over time.^{74,75} The alternative Fine and Gray approach⁷⁶ models the effect of treatment on the subdistribution hazard or directly on the cumulative incidence function. While we will consider this and compare its fit to the model-free cumulative incidence curves,⁷⁵ the proportional hazards approach will be our primary analysis.

Similar analyses will be conducted for both cancer and CVD. For cancer, we will estimate the intervention effects on the primary endpoint of total cancer, as well as the secondary outcomes of breast, prostate, and colorectal cancer, and cancer mortality. For CVD we will estimate the effects on the primary composite endpoint of major CVD (MI, stroke, and cardiovascular mortality); on the secondary composite endpoint that additionally includes coronary revascularization; and on the individual components of MI, stroke, revascularization, and cardiovascular mortality.

Beyond the primary analyses, we will conduct prespecified secondary analyses to examine effect modification by the other randomized intervention, by baseline risk factors, by compliance, and by time. We have a particular interest in exploring interactions between the interventions, as well as with the baseline plasma biomarkers of 25(OH)D for vitamin D and of EPA+DHA for fish oil. We hypothesize that the intervention effects may be larger among those with below-median baseline levels, and will examine treatment effects by quartiles of these biomarkers. The biomarker data will be analyzed as a case-cohort study using methods for proportional hazards regression.⁷⁷ Because of the frequency matching by age and gender, appropriate stratum-specific weighting of the observations will be employed.⁷⁸ We also have a prior interest in the effects of the vitamin D intervention within groups defined by race/ethnicity and skin

pigmentation, and by BMI. In addition, we will evaluate effect modification by age and gender, as well as by sunlight exposure, calcium and phosphorus intakes from the FFQ (as these nutrients affect vitamin D bioavailability⁷⁹), and baseline risk factors for cancer and CVD. The latter interaction effects will be interpreted cautiously, as hypothesis generating. We will also examine as a prespecified secondary analysis the association among compliers, in which participants' follow-up time will be censored when they are no longer compliant with taking at least two-thirds of their assigned active agents or placebos. Finally, we will examine whether treatment effects vary over time and duration of treatment by examining survival plots and interactions with time. We will additionally conduct analyses for the primary endpoints of cancer and cardiovascular disease excluding events occurring in Year 1, as well as in Years 1 and 2, of follow-up. There may be a latent effect on both outcomes, depending on the mechanisms by which these agents act.

We will also compare the incidence of potential side effects in the active v. placebo groups for each agent, including the incidence of kidney stones with vitamin D assignment (cf. WHI calcium-vitamin D findings⁴⁴) and the incidence of GI symptoms, skin abnormalities, and bleeding with fish oil assignment (cf. JELIS findings⁴¹).

B. POWER CALCULATIONS

To calculate power, the following assumptions were made: (1) a 2x2 factorial trial in 12,500 men aged ≥ 50 and 12,500 women aged ≥ 55 ; (2) independent and equal allocation of participants to each treatment; (3) an age distribution based on that observed at baseline in our past trials for men aged ≥ 50 and women aged ≥ 55 ; (4) age-specific event rates based on the observed rates in the first 5 years of the PHS II for men and the WHS for women; (5) trial follow-up of 5 years, with little loss to follow-up as achieved in our past trials; and (6) compliance similar to that in published trials upon which our estimated rate ratio (RR) reductions are based. The cited reductions are thus the observed effects we would see in the trial. The corresponding 'true' RR is given assuming an average compliance of 80%. Power is given for a two-sided test using a logrank analysis⁸⁰ with a significance level of 0.05.

Cancer: Assuming that only one agent is effective, with 5 years of treatment and follow-up we will have 93% power to detect an observed RR of 0.85 for the primary endpoint of total cancer incidence (Table 1). For prostate cancer, we will have 93% power to detect a 25% risk reduction. For breast cancer, we will have 86% power to detect a 35% risk reduction. For colorectal cancer, we will have 77% power to detect a 35% risk reduction and 88% power to detect a 40% risk reduction. For cancer mortality, we will have 86% power to detect a 30% risk reduction. If both agents are effective in preventing cancer but act independently, power would be reduced slightly due to a somewhat smaller overall

Table 1. Power for effects of a single agent on cancer in VITAL, a 2x2 factorial trial of 12,500 men aged ≥ 50 and 12,500 women aged ≥ 55 , with 5 years of follow-up

Observed RR ^a	True RR ^b	Total Cancer	Cancer Mortality	Colorectal Cancer	Breast Cancer (Women)	Prostate Cancer (Men)
0.90	0.875	61.4	-	-	-	-
0.85	0.812	92.7	-	-	-	-
0.80	0.750	99.6	50.5	31.7	38.7	77.0
0.75	0.687	>99.9	70.6	46.8	56.3	92.8
0.70	0.625	>99.9	86.1	62.9	73.2	98.6
0.65	0.560	>99.9	95.0	77.3	86.3	99.8
0.60	0.500	>99.9	98.7	88.2	94.3	>99.9

a. Observed RR=intent-to-treat RR, including noncompliant participants. Compliance is assumed to be 80%.
b. True RR=that with perfect compliance.
RR, rate ratio.

number of events. If the agents interact, however, power will be affected to the extent of the interaction. Should the agents act synergistically, power would increase, as illustrated in Table 2 for the outcome of total cancer.

For example, if the effect of each agent alone is a reduction of 10%, but in combination the effect is stronger, with an additional 10% decrease, the RR comparing the combined group to the all placebo group would be 0.73, versus 0.81 with additive effects (on the multiplicative scale). Power for the main effect of each agent would then increase to 88% (or higher with greater synergy). The trial would have power to detect moderate-to-large interactions, as shown in Table 2. Should the agents interact in a subadditive fashion, power would be reduced to the extent of the subadditivity. Power to explore effect modification by baseline blood levels of

Table 2. Power for effects of a single agent on CVD in VITAL, a 2x2 factorial trial of 12,500 men aged ≥ 50 and 12,500 women aged ≥ 55 , with 5 years of follow-up

Observed RR ^a	True RR ^b	Major CVD ^c	Total CVD ^d	CVD Mortality		
				MI	Stroke	
0.90	0.875	41.6	62.2	-	-	-
0.85	0.812	75.6	93.2	-	-	-
0.80	0.750	94.8	99.6	53.7	60.1	60.3
0.75	0.687	99.5	>99.9	74.0	80.2	80.3
0.70	0.625	>99.9	>99.9	88.7	92.8	92.8
0.65	0.560	>99.9	>99.9	96.3	98.2	98.2
0.60	0.500	>99.9	>99.9	99.2	99.7	99.7

a. Observed RR=intent-to-treat RR, including noncompliant participants. Compliance is assumed to be 80%.
b. True RR=that with perfect compliance.
c. Major CVD=myocardial infarction, stroke, and CVD mortality
d. Total CVD=myocardial infarction, stroke, CVD mortality, and coronary revascularization (coronary artery bypass grafting or percutaneous coronary intervention)
CVD, cardiovascular disease; MI, myocardial infarction; RR, rate ratio.

25(OH)D and EPA+DHA among those above and below the median level in the cohort will be lower because we anticipate that about 60% of participants will provide blood specimens.

Power has been shown for a given observed reduction in risk, assuming compliance

similar to that seen in current randomized trials such as the WHS and PHS. For total cancer, our power will be excellent with a 5-year follow-up even if compliance is lower.

CVD: As shown in Table 3, assuming that only one agent is effective, with 5 years of treatment and follow-up we will have 95% power to detect an observed RR of 0.80 for the primary composite endpoint of MI, stroke, and cardiovascular mortality. For the secondary composite endpoint of MI, stroke, cardiovascular mortality, and coronary revascularization, we will have over 99% power to detect a 20% reduction and 93% power to detect a 15% reduction. With a RR of 0.70 we will have 89% power for cardiovascular mortality, and we will have over 80% power to detect an RR of 0.75 for MI and stroke. If both agents are effective in preventing CVD but act independently, power would be reduced only slightly due to

Table 3. Power for interaction effects on total cancer in VITAL, a 2x2 factorial trial of 12,500 men aged ≥ 50 and 12,500 women aged ≥ 55 , with 5 years of follow-up

RR Single agent ^a	Interaction ^b	RR Both agents	Power	
			Main Effect	Interaction
0.90	1.0	0.81	59.1	
	0.9	0.73	88.4	
	0.8	0.65	98.5	60.7
	0.7	0.57	99.9	93.6
0.85	1.0	0.72	90.6	
	0.9	0.65	98.6	
	0.8	0.58	99.9	57.8
	0.7	0.51	>99.9	92.0
0.80	1.0	0.64	99.2	
	0.9	0.58	99.9	
	0.8	0.51	>99.9	54.7
	0.7	0.45	>99.9	89.9

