Run-in: The experience of other studies conducted by our research group (PHS, WHS, and WAFACS) has demonstrated the success of a run-in period in identifying a group of excellent compliers for long-term follow-up. Because the health experience of participants will be analyzed according to randomized treatment assignment, the use of a run-in phase to eliminate poor compliers prior to randomization will increase the power of the study.⁴⁶ During a 3-month run-in period, all participants will take placebo vitamin D softgel capsules and placebo fish oil. As the effects of both agents on cancer prevention are likely to be chronic, it would not be scientifically appropriate to use active agent in the run-in and then randomize to placebo. Moreover, the use of placebos will allow us to most clearly analyze the side effects of the study agents during the randomized treatment period.

At trial enrollment, willing and eligible participants will be mailed a 6-month supply of run-in calendar packs (i.e., 3 months for the actual run-in and 3 months to allow pill-taking to continue uninterrupted while we check participants' responses for continued eligibility and then ship randomized capsules to participants who remain eligible). Participants will take two capsules per day (one vitamin D placebo softgel capsule and one fish oil placebo capsule). At 3 months, participants will receive a follow-up run-in questionnaire asking about continued eligibility,

willingness to continue in the trial, pill compliance, and potential side effects. Non-responders will be mailed up to 3 requests at 6-week intervals.

Participants will be randomized only if they: (1) demonstrate good compliance in pill taking, defined as taking at least two-thirds of the study pills during the run-in (i.e., missed 10 or fewer days of pill taking in the past month); (2) express willingness to continue in the trial; (3) report no new history of cancer (except non-melanoma skin cancer), MI, stroke, TIA, CABG, PCI, hypercalcemia, sarcoidosis, kidney failure or dialysis, parathyroid disease, cirrhosis or other severe liver disease, or other serious illness, use of anticoagulants or vitamin D analogues, during the run-in; (4) are consuming no more than 1200 mg/d of calcium (the RDA for men aged >70 years and women aged >50 years²) from all supplemental sources combined; and (5) demonstrate continued willingness to limit supplemental vitamin D intake to ≤ 800 IU/d and to forego the use of fish oil supplements.

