With regard to follow-up, at 6 months, participants will be mailed a very brief follow-up questionnaire and at each anniversary date a more detailed questionnaire and a re-supply of calendar packs. The questionnaire will include items on compliance with randomized treatments, use of non-trial supplements of vitamin D and fish oil, use of calcium supplements, development of major illnesses, dietary intakes of vitamin D and fish, and updated risk factors related to cancer and CVD. Information on potential side effects of the study agents will be elicited for monitoring by the Data and Safety Monitoring Board. For fish oil, these side effects include GI symptoms (burping, stomach upset or pain, nausea, constipation, diarrhea), bleeding (any GI bleed, GI bleeding, hematuria, easy bruising, epistaxis), skin rash, colds or upper respiratory tract infection, flu-like symptoms, and bad taste in mouth. For vitamin D, these side effects include GI symptoms, and physician diagnosis of hypercalcemia or kidney stones, both of which are not expected to occur at the dose used in VITAL.² Non-responders will be mailed a second and third request and will then be telephoned to collect study data. If phone contact fails, a fourth request will be mailed in order to ascertain the participant's study status and to obtain minimum information regarding the primary study outcomes. Participants will also be given the option of completing an electronic questionnaire sent via e-mail. These data will be collected and managed using REDCap electronic data capture tools. REDCap (Research Electronic Data Capture) is a secure, HIPAA-compliant web-based application hosted by PartnersHealthCare Research Computing.

Internet sources will be used to assist in the tracking (new address, new phone number) of participants who are potentially lost to follow-up. At the very least, vital status will be ascertained. Participants will be instructed to discontinue their study capsules if, during follow-up, they receive a diagnosis of hypercalcemia, sarcoidosis, or other safety-exclusion conditions and to inform their physicians about their participation in VITAL. If, in the course of follow-up,

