Potential side effects of the study agents will be assessed on each follow-up questionnaire. For fish oil, these side effects include gastrointestinal (GI) symptoms (burping, stomach upset or pain, nausea, constipation, diarrhea), bleeding (any GI bleed, GI bleeding requiring transfusion, hematuria, easy bruising, epistaxis), skin rash, colds or upper respiratory tract infection, flu-like symptoms, and bad taste in mouth. A recent study reported that men with high blood levels of omega-3 fatty acids, which are found in fish and fish oil supplements, were more likely to develop prostate cancer than men with low blood levels of omega-3 fatty acids.⁸¹ However, because this was an observational study and not a randomized trial, the findings could be spurious, resulting from confounding bias. The VITAL trial will be collecting information on new diagnoses of prostate cancer, assessed on each follow-up questionnaire by self-report and confirmed on medical record review. For vitamin D, side effects include GI symptoms; and physician diagnosis of hypercalcemia or kidney stones, both of which are not expected to occur at the dose used in VITAL.²

There is also the possibility of social/psychological risk that could result from inadvertent disclosure of confidential information from the questionnaires or blood tests. However, we have many safeguards in place to avoid this possibility, and we have never had an inadvertent breach of confidentiality in any of our trials.

With regard to the risks of the study agents, information on potential side effects discussed above will be elicited on each follow-up questionnaire for monitoring by the Data and Safety Monitoring Board. We will compare the incidence of potential side effects in the active v. placebo groups for each agent, including the incidence of kidney stones with vitamin D assignment and the incidence of GI symptoms, skin abnormalities, and bleeding with fish oil assignment.

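### The side-effect comparison makes no use of the on-placebo side-effect report collected from every participant before randomization, and so gives up precision at no saving

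*Combined protocol and SAP*

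**What the plan says.** In the final protocol, section IV (Run-in), "all participants will take placebo vitamin D softgel capsules and placebo fish oil" for 3 months. They then complete a questionnaire on continued eligibility, "willingness to continue in the trial, pill compliance, and potential side effects". The same section gives as one reason for a placebo run-in that "the use of placebos will allow us to most clearly analyze the side effects of the study agents during the randomized treatment period".

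After randomization, according to section VII, "Potential side effects of the study agents will be assessed on each follow-up questionnaire". Many of the listed items are non-specific symptoms. For fish oil, section V.D begins with "GI symptoms (burping, stomach upset or pain, nausea, constipation, diarrhea" and goes on to easy bruising, rash, colds and bad taste.

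The analysis is one sentence in VI.A of the final SAP, repeated in VI.A of the final protocol: "We will also compare the incidence of potential side effects in the active v. placebo groups for each agent". Section VII of the protocol says the same: "We will compare the incidence of potential side effects in the active v. placebo groups for each agent". None of these places defines an incident side effect, names an effect measure or model, or mentions the run-in report. The baseline table in VI.A does not include it either: "Characteristics to be examined include known risk factors for cancer and CVD", followed by such factors and nutrient levels. The efficacy endpoints, by contrast, have a named Cox model with covariates.

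**The concern.** The run-in answer is a pre-randomization measurement, taken on placebo, of the kind of symptom later compared by arm. Someone who had stomach upset or easy bruising on placebo is much more likely than others to report it again, in either arm. A comparison that ignores this leaves predictable variation in the error term.

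If recurrences count as events and the agent acts mainly on new onset, those recurrences also add equally to both arms and pull the risk ratio toward 1. In a safety comparison, lost precision and attenuation both make a real side effect harder to see. Protocol section IX.A states the trial's goal as the overall balance of benefits and risks.

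**Working it through.** **Plan's own figure.** There is none. The documents give no rate, effect size or power for side effects, so the following is an illustration under assumed rates.

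**Inputs from the documents.** 26,500 participants (final protocol, III) allocated equally for each agent (VI.B), so n = 26,500 / 2 = 13,250 per arm. The two-sided 0.05 level is borrowed from the efficacy power section.

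**Assumed inputs.** q = 20% report the symptom at run-in; r = 80% of those on placebo report it again; i = 10% new onset on placebo; R = 1.10, the risk ratio in run-in-negatives; ρ, the risk ratio in run-in reporters, set to 1.00 (no effect), 1.05 (half the excess) or 1.10 (same effect). Reports over follow-up are collapsed to any report or none.

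**Formulas.**
- Placebo risk a = q r + (1−q) i = 0.16 + 0.08 = 0.24.
- Active risk b = q r ρ + (1−q) i R.
- Unadjusted z = (b − a) / √{[a(1−a) + b(1−b)] / n}.
- Stratified z = [q d1 + (1−q) d2] / √[q² v1 + (1−q)² v2]. Here d1 and d2 are the risk differences in run-in reporters (2,650 per arm) and run-in-negatives (10,600 per arm), and v1 and v2 are their variances.
- Power = Φ(z − 1.96).

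**Worked case, ρ = 1.00.** b = 0.16 + 0.8 × 0.11 = 0.248, so the difference is 0.008 and the observed risk ratio is 0.248 / 0.24 = 1.033.
- Unadjusted: SE = √[(0.1824 + 0.1865) / 13,250] = 0.00528; z = 1.52.
- Stratified: v1 = (0.16 + 0.16) / 2,650 = 0.0001208; v2 = (0.09 + 0.0979) / 10,600 = 0.00001773. The variance is 0.04 × 0.0001208 + 0.64 × 0.00001773 = 0.00001618; SE = 0.00402; z = 1.99.
- Run-in-negatives only: z = 0.01 / √0.00001773 = 2.38. This does not depend on ρ.

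| Effect in run-in reporters | b | Unadjusted z (power) | Stratified z (power) | Run-in-negatives only, z (power) |
|---|---|---|---|---|
| none, ρ = 1.00 | 0.248 | 1.52 (32.9%) | 1.99 (51.2%) | 2.38 (66.1%) |
| half the excess, ρ = 1.05 | 0.256 | 3.02 (85.5%) | 4.03 (98.1%) | 2.38 (66.1%) |
| same, ρ = 1.10 | 0.264 | 4.50 (99.4%) | 6.13 (>99.9%) | 2.38 (66.1%) |

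The squared ratio of stratified to unadjusted z is the equivalent gain in sample size: (1.99/1.52)² ≈ 1.7, (4.03/3.02)² ≈ 1.8 and (6.13/4.50)² ≈ 1.9.

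**Wider grid.** Take q = 10, 20 or 30%; r = 70 or 80%; i = 10 or 25%; R = 1.10 or 1.20: 24 combinations. The stratified z exceeds the unadjusted z in all 24 under each of the three assumptions about ρ. In the six combinations with R = 1.10 and i = 10%, restriction to run-in-negatives gives 60–71% power. The unadjusted comparison there gives 23–51% (no effect in reporters), 78–91% (half the excess) or 94% to over 99% (same effect).

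**The case against.** **The plan states no wrong rule.** A reader might infer that pre-existing symptoms will be counted as events. The text does not say so. Incidence can be read as new onset, and the plan is silent on which is meant. This objection stands, and attenuation is therefore conditional on recurrences being counted. If new onset was intended, the plan still has to name the baseline that defines it, and the run-in report is the obvious one.

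**Validity is intact.** Randomization balances run-in symptoms in expectation, and with no effect both arms have the same risk. There is no confounding and no inflated false-positive rate. The unadjusted difference is also a legitimate estimate for any report in the whole randomized population. This stands: the loss is in precision and, conditionally, in the size of the estimate.

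**Excluding run-in reporters is not a safe remedy.** It looks attractive only if the agent leaves those people unaffected. If they are the susceptible ones, exclusion discards real harm events and loses power, as the table shows. This stands, and it rules out restriction as the main analysis. It does not touch the stratified analysis.

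**Not every harm is concerned.** New hypercalcemia during the run-in bars randomization (protocol IV). A new physician-diagnosed kidney stone or a transfused GI bleed is a discrete event. A claim that any harm signal is diluted would go too far.

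**The run-in form is not shown.** Its items and wording are unknown, so the remedy can cover only symptoms asked about both then and later.

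**The gain can be small.** At 25% new onset and R = 1.10, unadjusted power is already 82–98% even with no effect in reporters. If a run-in report did not predict later reports, stratifying would gain nothing.

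**Conclusion.** The point holds as a nearly free improvement, limited to self-reported, recurrent symptoms: GI symptoms, easy bruising, rash, colds and bad taste. The planned comparison is valid but ignores a baseline value the trial already collects from everyone. Stratifying by it raises precision whether or not the agent affects people symptomatic at run-in. In the illustrated case, power goes from about 33% to 51% or from about 85% to 98%, depending on that effect.

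These figures rest wholly on assumed prevalence, recurrence and onset rates. With the stratum-size weights used here, the all-participant risk difference is unchanged and only its standard error shrinks. The new-onset effect has to be read from the run-in-negative stratum. The sentence in section IV about analyzing side effects clearly explains why placebo rather than active agent is used in the run-in. It should not be read as a commitment to use the run-in report.

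**What to change.** In VI.A of the SAP and protocol:

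1. For each self-reported side effect that the run-in form also asks about, define the outcome and name the effect measure. Make the main active versus placebo comparison an all-participant analysis stratified by, or adjusted for, the run-in report, controlling for the other agent and age group.
2. Report new onset among participants without that symptom at run-in as a supplementary estimate only, noting that it does not apply to people symptomatic at run-in and can miss harm in them.
3. Give the DSMB the same stratified table.

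The cost is a few sentences of SAP text, a check of which items the run-in and follow-up forms share, and a little programming. It needs no new data collection and changes no treatment, visit or efficacy analysis.
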